**Section F Cold chain and transport**  
(Complete this section by asking and/or observing practice)

Last vaccine storage point:	
• Is the temperature of the vaccine storage refrigerator monitored?	Yes / No
○ If “yes”, was there any deviation outside of 2–8° C after the vaccine was placed inside?	Yes / No
○ If “yes”, provide details of monitoring separately.	
• Was the correct procedure for storing vaccines, diluents and syringes followed?	Yes / No / Unkn
• Was any other item (other than EPI vaccines and diluents) in the refrigerator or freezer?	Yes / No / Unkn
• Were any partially used reconstituted vaccines in the refrigerator?	Yes / No / Unkn
• Were any unusable vaccines (expired, no label, VVM at stages 3 or 4, frozen) in the refrigerator?	Yes / No / Unkn
• Were any unusable diluents (expired, manufacturer not matched, cracked, dirty ampoule) in the store?	Yes / No / Unkn
Specific key findings/additional observations and comments:	
Vaccine transportation:	
• Type of vaccine carrier used	
• Was the vaccine carrier sent to the site on the same day as vaccination?	Yes / No / Unkn
• Was the vaccine carrier returned from the site on the same day as vaccination?	Yes / No / Unkn
• Was a conditioned ice-pack used?	Yes / No / Unkn
Specific key findings/additional observations and comments:	

**Section G Community investigation (Please visit locality and interview parents/others)**

Were any similar events reported within a time period similar to when the adverse event occurred and in the same locality? Yes / No / Unknown If yes, describe:
If yes, how many events/episodes?
Of those effected, how many are
• Vaccinated: _____
• Not vaccinated: _____
• Unknown: _____
Other comments:

**Section H Other findings/observations/comments**

--

## Annex 19: AEFI Causality Assessment Worksheet

### Step 1: Eligibility

Name of the patient	Name of one or more vaccines administered before this event	What is the valid diagnosis?	Does the diagnosis meet a case definition?

**Create your question on causality here**

[figure not shown]
Has the \_\_\_\_\_ vaccine/vaccination caused \_\_\_\_\_? (The event is for review in step 2)

I. Is there strong evidence for other causes?	Y N UK NA	Remarks
Does a clinical examination, or laboratory tests on the patient, confirm another cause?	□ □ □ □	
II. Is there a known causal association with the vaccine or vaccination?		
Vaccine product(s)		
Is there evidence in the literature that this vaccine(s) may cause the reported event even if administered correctly?	□ □ □ □	
Did a specific test demonstrate the causal role of the vaccine or any of the ingredients?	□ □ □ □	
Immunization error		
Was there an error in prescribing or non-adherence to recommendations for use of the vaccine (e.g. use beyond the expiry date, wrong recipient etc.)?	□ □ □ □	
Was the vaccine (or any of its ingredients) administered unsterile?	□ □ □ □	
Was the vaccine's physical condition (e.g. colour, turbidity, presence of foreign substances etc.) abnormal at the time of administration?	□ □ □ □	
Was there an error in vaccine constitution/preparation by the vaccinator (e.g. wrong product, wrong diluent, improper mixing, improper syringe filling etc.)?	□ □ □ □	
Was there an error in vaccine handling (e.g. a break in the cold chain during transport, storage and/or immunization session etc.)?	□ □ □ □	
Was the vaccine administered incorrectly (e.g. wrong dose, site or route of administration; wrong needle size etc.)?	□ □ □ □	
Immunization anxiety		
Could the event have been caused by anxiety about the immunization (e.g. vasovagal, hyperventilation or stress-related disorder)?	□ □ □ □	
II (time). If "yes" to any question in II, was the event within the time window of increased risk?		
Did the event occur within an appropriate time window after vaccine administration?	□ □ □ □	
III. Is there strong evidence against a causal association?		
Is there strong evidence against a causal association?	□ □ □ □	
IV. Other qualifying factors for classification		
Could the event occur independently of vaccination (background rate)?	□ □ □ □	
Could the event be a manifestation of another health condition?	□ □ □ □	
Did a comparable event occur after a previous dose of a similar vaccine?	□ □ □ □	
Was there exposure to a potential risk factor or toxin prior to the event?	□ □ □ □	
Was there acute illness prior to the event?	□ □ □ □	
Did the event occur in the past independently of vaccination?	□ □ □ □	
Was the patient taking any medication prior to vaccination?	□ □ □ □	
Is there a biological plausibility that the vaccine could cause the event?	□ □ □ □	

Note: Y: Yes; N: No; UK: Unknown; NA: Not applicable.

**Step 3: Algorithm**

Review all steps and check ✓ all the appropriate boxes

Notes for step 3:

**Step 4: Classification**

Check ✓ all boxes that apply

Adequate information available	
A. Consistent causal association to immunization
 
 A1. Vaccine product-related reaction (As per published literature)
 
 A2. Vaccine quality defect-related reaction
 
 A3. Immunization error-related reaction
 
 A4. Immunization anxiety-related reaction
			
B. Indeterminate
 
 B1. *Temporal relationship is consistent but there is insufficient definitive evidence for vaccine causing event (may be new vaccine-linked event)
 
 B2. Reviewing factors result in conflicting trends of consistency and inconsistency with causal association to immunization
	
C. Inconsistent causal association to immunization
 
 C. Coincidental Underlying or emerging condition(s), or conditions caused by exposure to something other than vaccine

	Adequate information not available	
 Unclassifiable
 
Specify the additional information required for classification:
			

\*B1: This is a potential signal and maybe considered for investigation

Summarize the classification logic:  
 With available evidence, we could conclude that the classification is \_\_\_\_\_ because:

Source: Causality assessment of adverse event following immunization (AEFI): User manual for the revised WHO classification. World Health Organization. 2013. ISBN 978 92 4 150533 8.  
[www.who.int/vaccine\\_safety/publications/gvs\\_aefi/en/](http://www.who.int/vaccine_safety/publications/gvs_aefi/en/)

In the phase 3 trial of the vaccine conducted from 2009 to 2014 [2], in children who received four vaccine doses (three primary doses and a fourth dose 18 months later), the incidence of uncomplicated malaria and of severe malaria were reduced by 39% and 32% respectively over 4 years of follow-up. For every 1000 children vaccinated with 4 doses, a total of 1774 cases of malaria and 40 hospital admissions due to malaria were averted over about 4 years¹. A total of 19 cases of severe malaria were averted, cases which, without the enhanced access to care provided in the context of the trial, might have led to death. The vaccine therefore could have a substantial public health impact.

The current vaccination schedules include three primary doses to be administered before 9 months of age and a fourth dose at about 2 years of age. This involves three to four additional vaccination visits than are currently recommended in this age range. The MVPE seeks to determine the impact realised in practice when the vaccine is introduced in areas of high to moderate malaria incidence in three countries with year-round malaria transmission. The programme will evaluate the safety of RTS,S/AS01 in routine use, the feasibility of administering four doses of the vaccine, and the impact of the vaccine at population level, using a cluster-randomized design. The vaccine is being introduced sub-nationally in pilot areas in each of the three countries, by the EPI programme. Within the pilot area in each country, districts (in Ghana), subcounties (in Kenya), and clusters of equivalent population (in Malawi), have been randomized to either introduce the vaccine in 2019 (implementation clusters), or to delay introduction until the initial introduction has been evaluated (comparison clusters). Thus, the evaluation will use a cluster-randomized design. Community reporters will document all deaths occurring in children under 5 years of age in the implementation and comparison clusters. Hospital surveillance is being established in sentinel hospitals in a subset of clusters to monitor the incidence of admission with malaria and other conditions. Vaccine administration will be delivered through, and monitored by, the Expanded Programme for Immunization (EPI) in each country and uptake of RTS,S/AS01 will also be measured independently through cluster-sample household surveys.

The MVPE will determine whether the introduction of RTS,S/AS01 leads to a reduction in child deaths, and a reduction in the incidence of hospital admission with severe malaria, over the 4 years of the implementation programme (MVIP, Malaria Vaccine Implementation Programme). The MVPE also addresses three safety signals that were observed in the phase 3 trial but whose significance was unclear: an unexplained excess of meningitis cases in RTS,S/AS01 recipients, an excess in cerebral malaria cases among RTS,S/AS01 recipients who developed severe malaria and, among the relatively small number of deaths that occurred in the trial, an excess of deaths among girls who received RTS,S/AS01 compared to girls who did not receive RTS,S/AS01. The data to be collected

¹ In the phase 3 trial, for every 1000 children vaccinated with 4 doses, a total of 1774 (95% CI 1387–2186) cases of malaria, 40 (95% CI 19–64) hospital admissions due to malaria, and 19 (95% CI 4 to 35) cases of severe malaria, were averted over about 4 years.

over 4 years will inform a policy decision about wider use of RTS,S/AS01 as a means to reduce malaria morbidity and mortality, when provided in addition to existing malaria control measures. It is anticipated that sufficient data to assess the safety signals are likely to be available after the first 2 years of the evaluation. At that time, all available data would be reviewed, including outcomes related to safety of the vaccine in routine use (meningitis, cerebral malaria, mortality by gender, AEFI), the impact on severe malaria and all-cause mortality, coverage of the first 3 doses, preliminary data on administration of the 4th dose, and cost-effectiveness assessment. A recommendation about wider use of the vaccine might therefore be made before final impact data are available, recognizing that the impact in any setting will depend on coverage and timeliness of vaccination and the malaria burden, which may differ from those in the MVIP [3].

2. Design of the evaluation

A total of 158 clusters, 66 in Ghana, 46 in Malawi and 46 in western Kenya, each cluster with a total population of about 100,000 on average, were randomized to either introduce RTS,S/AS01 vaccine in 2019 or to delay introduction until a decision is reached about safety and effectiveness.

Throughout the evaluation areas, surveillance will be maintained to record all deaths in children under the age of 5 years. This will be done by community reporters who will record date of death, date of birth, age at death, gender, and residence location. The reporters will notify project staff who will visit the home of each child who has died to complete a verbal autopsy (VA). VAs will be completed for all deaths under 5 years of age. The purpose of the VA is to confirm key details (that the death occurred, the date of death and age at death, gender, where the child was living at the time of death and their normal place of residence if different), and to establish the likely cause of death. Causes of death will be determined from the VAs by three independent physicians or computer algorithm. An important purpose of assigning causes of death (in children in vaccine-eligible age groups) will be to be able to exclude deaths due to injury from the analysis of effects of the malaria vaccine on overall mortality. At the time of the verbal autopsy (and if possible from the card by the local reporter) vaccination status will also be recorded, copying details from the home-based record (HBR) and completing a questionnaire to elicit caregiver recall about vaccinations. . In some circumstances, a limited VA will be performed instead of a full VA, collecting only the key details, without determining cause of death, other than determining death was due to accident or injury.

Surveillance for severe illness, with a focus on meningitis and severe malaria, will be maintained in part of the evaluation area in each country, through 18 sentinel hospitals, 8 in Ghana, 4 in Malawi and 6 in Kenya. These hospitals draw patients from a subset of clusters. The combined catchment areas include 32 of the clusters in Ghana, 17 clusters in Malawi, and 28 clusters in Kenya. Details of all inpatients aged 1 to 59 months will be captured, including residence location at the time of admission and their normal place of residence if different, date of admission, age at admission, date of birth, gender, final diagnosis, outcome (died or discharged alive), and clinical and laboratory details (for suspected cases of meningitis and severe malaria). Vaccination status will also be recorded for all admissions, copying details from the home-based record (HBR) or completing a questionnaire to elicit caregiver recall about vaccinations.

Table 1: Number of clusters randomized in each country, number of surveillance hospitals, and the number of clusters within the catchment of the sentinel hospitals

Country	Clusters	Population: annual birth cohort mean (range)	Sentinel Hospitals	Clusters in sentinel hospital catchments	Catchment clusters: annual birth cohort mean (range)
Ghana	66	3975 (912,8954)	8	32	4628 (1202,8954)
Kenya	46	5488 (2702,10739)	6	28	5559 (3487,10739)
Malawi	46	4820 (2816,8112)	4	17	5115 (2816,8112)
TOTAL	158	4661	18	77	5074

(excludes areas where the GSK phase 4 study is being done in each country)

Hospital and mortality surveillance will start when RTS,S/AS01 vaccination begins, or as soon as possible after that date, and be maintained until 46 months from the start of RTS,S/AS01 vaccination.

Administration of doses of RTS,S/AS01 and of other vaccines will be recorded by the EPI programme in each country using their normal record keeping system. Vaccination coverage will also be measured independently through community surveys. A survey will be undertaken at baseline, to measure coverage of EPI vaccines and Vitamin A, deworming treatment, malnutrition by MUAC, and the prevalence of *P.falciparum* infection (using an HRP2 Rapid Diagnostic Test). A second survey will be undertaken after about 18 months to measure coverage of EPI vaccines and, in RTS,S clusters, coverage of 1,2 and 3 doses of RTS,S in children 12-23 months of age. A third survey is planned to measure coverage of the fourth dose of RTS,S.

The MVPE was designed to detect differences in disease and mortality rates, over 46 months, between RTS,S and comparison clusters. Specifically, it was powered to detect a reduction in all-cause mortality in each country in RTS,S clusters of 10% or more (with 90% power) ; to detect a 2.6-fold or greater increase in the rate of meningitis (all countries combined) with 90% power ; to detect an increased incidence of cerebral malaria if the true rate is increased by 1.7-fold or more; and to detect an increase in the female:male mortality ratio with 90% power if the ratio is increased by 1.15-fold or more.

3. Description of the clusters

In Ghana, the clusters are districts, immunization clinic catchments fall entirely within single districts. In Malawi, clusters do not correspond to existing administrative units (no suitable existing units could be identified). Clusters were defined by allocating 187 health facilities that administer childhood vaccinations, into 46 groups of adjacent facilities, the combined catchment areas of each group having approximately the total population required for the evaluation. In Kenya, clusters correspond to subcounties.

4. Randomization

A separate document describes the randomization in detail [4]. The EPI programme in each country led the process of randomization and vaccine introduction. WHO provided technical assistance to assure unbiased randomization options. In each country the Ministry of Health held a public event to select the final randomization option. Randomization options were prepared using constrained randomization, which aimed to ensure implementation and comparator clusters were similar with respect to factors related to malaria burden, access to care and to immunisation services, whilst retaining a substantial element of chance in the allocation of each cluster. This is important so that the process remains fair and the observations in each cluster can be considered independent, an assumption for normal methods of statistical analysis to remain valid.

Randomization in each country was limited to permutations for which implementation and comparator areas would have clusters of similar population size, EPI coverage, and malaria transmission intensity would be similar in, and such that there would be a similar number of health facilities [4]. In addition, in Kenya and in Malawi, there was the geographic constraint that each county (in the case of Kenya) and each district (in Malawi) should have at least one cluster allocated to implement the RTS,S vaccine. Lastly, clusters containing a sentinel hospital were to be equally divided between RTS,S and comparator arms. A further constraint, that a measure of the number of hospital admissions from each cluster in the catchment of each hospital should be balanced between RTS,S and comparator clusters, was considered and was applied to some hospitals but not to all as this would have resulted in an overly constrained design. Catchment areas as defined, are also served by other facilities, thus the sentinel hospitals capture a proportion of hospital admissions in the defined areas.

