### 8.2.2 Secondary impact objectives

The secondary objectives of the impact evaluation are to estimate the effect of routine delivery of RTS,S/AS01 on incidence hospital admission with cerebral malaria

- the incidence of hospital admission with severe malaria anaemia (patients admitted, who had severe malaria anaemia)
  - incidence of all-cause hospital admission
  - incidence of non-malaria hospital admission
  - incidence of cause-specific hospital admission
  - incidence of the requirement for or provision of blood transfusions
  - cause-specific mortality (from verbal autopsy or hospital diagnosis)
  - malaria-specific mortality in hospital
  - all-cause mortality, excluding deaths due to trauma or accidents
  - malaria-specific mortality in hospital in boys and in girls

in children eligible to receive the vaccine, in each country and overall.

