### 9.3 Variables

The following variables, at a minimum, will be recorded for each identified death: date of birth, date of death, age at death, gender, place of normal residence, longitude and latitude of the place of normal residence, place of death if different, whether cause of death was illness, or due to accident or trauma, and dates of each dose of each vaccination (BCG, OPV, DTP (or DTP/HepB/Hib, as appropriate), measles and RTS,S/AS01), when available. The vaccination history will be captured from the child's health card wherever possible. A photograph of the health card may be taken and stored with the child's CRF to facilitate validation of vaccinations received and dates. Where no health card is available the information will be solicited from the caregiver via maternal recall (no dates) and documented as such. When vaccination information is collected through maternal recall, the caregiver/mother be asked about each vaccine (per country-specific EPI guidelines) and the number of doses, with detailed prompts characterizing the vaccines to enhance the quality of the recall (e.g., describing oral polio vaccine as bitter drops; etc.). In a subset of cases, parents may be asked additional questions to validate maternal recall. A validation study should be conducted in each country to understand the reliability of malaria vaccination status from different sources for children who have died, by comparing vaccination status from the home-based record, and from caregiver recall, with records at the immunization clinic. The distance to the nearest health facility, and distance from the nearest hospital will be calculated. Verbal autopsy will be performed for all children aged 1 – 59 months at the time of death. Verbal autopsy will follow the recommended WHO protocol using the 2016 WHO verbal autopsy instruments but including data on vaccination history (record-based and/or recall). Cause of death will be assigned using the WHO-recommended approach, currently the analytical software InterVA. Other methods (such as IHME's tariff method using the SmartVA application) can also be run on WHO VA 2016. Annex 7 presents the list of causes of death according to the VA procedure. Consent for the VA will be documented; if consent for the VA is not provided, the basic details of the death will be reported but cause of death and other details will not be available. If no information is available about the death that enables the VA classification, the cause of death will be classified as "CAUSE OF DEATH UNKNOWN".

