#### 9.4 Data sources

The analysis will include all deaths in the target age group, recorded by VRs. Cause-specific mortality analyses will draw on the results of VAs performed by VR supervisors and processed by InterVA or other WHO-recommended VA-coding process.

The denominators will be estimated using one of the approaches described in section 9.3 for the whole of the pilot implementation area in each country. Time at risk will be based on the estimated denominator and may be adjusted for seasonal variation in births.

The number of children receiving vaccines will be obtained from the MoH's vaccination registries.

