## 10.4 Case definitions

### 10.4.1 Meningitis

Meningitis was identified as a potential risk during the RTS,S/AS01 phase 3 study and particular efforts will be made to identify meningitis cases, defined in line with WHO's meningitis surveillance guidelines. For all cases with a diagnosis of meningitis, and a sample of non-meningitis diagnoses, an independent expert review, blinded to vaccine status, may be conducted on the patient's record (this is dependent on the ability to conduct a record review beyond the CRF) before a final diagnosis is provided. This is required to manage, in a standardised way across the MVPE, the potential confusion between meningitis and other severe illnesses, such as cerebral malaria.

Table 6 summarises the meningitis case definitions. **“Suspected meningitis”** is a diagnosis based on clinical symptoms and/or signs defined as:

*A child with one or more of the following present (with or without fever , neck stiffness, two or more seizures in the last 24 hours, bulging fontanelle, convulsions (partial, complex febrile or other atypical presentations), seizures if less than 6 months or greater than 6 years , altered consciousness, (Blantyre Coma Score less than 3 or, Glasgow Coma Score less than 11 or P or U on the AVPU scale [Alert Verbal Painful Unresponsiveness Scale]) or any other clinical symptoms indicative of meningitis or cerebral malaria by clinical judgement. Lumbar puncture will be encouraged in all such children, according to national diagnostic and treatment guidelines, for examination of cerebrospinal fluid (CSF).*

Children will be considered to have “**probable meningitis**” if:

*In a suspected case, the macroscopic aspect of the CSF is turbid, cloudy or purulent; or the CSF leukocyte count is >10 cells/mm^3.*

A child will be classified as a “**confirmed meningitis**” case if:

*A suspected or probable case is laboratory confirmed by culturing or identifying (i.e. by polymerase chain reaction) bacterial, viral or other aetiology in the CSF.*

Table 6: Meningitis case definitions for the MVPE

Clinical signs & laboratory results	In-country meningitis category	Results from Reference lab	Final meningitis category for analysis
[No neck stiffness AND (No altered consciousness OR alternative explanation for altered consciousness) AND No other meningeal sign*]	Not a meningitis case	Not needed for definition	Not a meningitis case

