10427	Was (s)he discharged from hospital very ill?	YES			
		NO			
		DK			
		Ref.			
10428	Had (s)he received immunisation?	YES			
		NO		➔	10432
		DK		➔	10432
		Ref.		➔	10432
10429	Do you have the child's vaccination card? (If no vaccination card, ascertain vaccinations through verbal recall)	YES			
		NO			
		DK			
		Ref.			
10430	Can I see the vaccination card (and note the vaccines the child received)? (If vaccination card can not be seen, ascertain vaccinations through verbal recall)	YES			
		NO			
		DK			
		Ref.			
10431	Note vaccines here (including RTS,S)				
	_____				
	_____				
	_____				
	_____				
10432	Was care sought outside the home while (s)he had this illness?	YES			
		NO		➔	10450
		DK		➔	10450
		Ref.		➔	10450

10433	Where or from whom did you seek this care?	traditional healer			
-------	--	--------------------	--------------------------	--	--

		homeopath			
		religious leader			
		government hospital			
		government health centre or clinic			
		private hospital			
		community-based practitioner associated with health system			
		trained birth attendant			
		private physician			
		Relative, friend (outside household)			
		pharmacy			
		Doesn't know			
		Refused to answer			
10434	Record the name and address of any hospital health centre or clinic where help was sought:				
	_____				
	_____				
	_____				
	_____				
10435	Did a health care worker tell you the cause of death?	YES			
		NO		➔	10437
		DK		➔	10437
		Ref.		➔	10437
10436	What did the health care worker say?				
	_____				

	_____				
	_____				
	_____				

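### SAP section 2 allows physicians to assign cause of death from verbal autopsies whose form records RTS,S status, and neither document masks those coders to status or arm

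*SAP*

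**What the plan says.** **Who assigns cause.** SAP section 2 (Design of the evaluation) states: "Causes of death will be determined from the VAs by three independent physicians or computer algorithm". The protocol does not mention physicians in this role. Its section 9.3 says: "Cause of death will be assigned using the WHO-recommended approach, currently the analytical software InterVA". Section 9.4 has the VAs "processed by InterVA or other WHO-recommended VA-coding process". The impact CRF in Annex 10 asks for the name of the coding algorithm and lists three software packages, with no physician option.

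**What the VA record holds.** Protocol 9.3 adopts the WHO 2016 instrument "but including data on vaccination history (record-based and/or recall". Annex 8, item 10431, reads "Note vaccines here (including RTS,S". SAP section 2 says: "At the time of the verbal autopsy (and if possible from the card by the local reporter) vaccination status will also be recorded". The form also has fields for usual residence, place of death and the facilities where care was sought (items 10055, 10057 and 10434).

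**Masking.** Neither document says that VA coders are masked to RTS,S status, cluster or arm. For hospital cases, protocol 10.4.1 says that "an independent expert review, blinded to vaccine status, may be conducted", and 10.4.2 says the same for severe malaria. Protocol 10.9 has the experts available to the DSMB start without knowledge of vaccine exposure.

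**Where the codes are used.** Protocol 8.2.2 lists "cause-specific mortality (from verbal autopsy or hospital diagnosis") among the secondary impact objectives. SAP section 2 describes removal of injury deaths from the mortality analysis as an important purpose of assigning cause.

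**The concern.** Choosing malaria rather than another febrile illness from a VA is a matter of judgement. A physician who reads that a child had a malaria vaccine may be less ready to code malaria, or may over-correct the other way. Either would be differential misclassification of the outcome by exposure.

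The planned analysis does not remove it. SAP section 6 compares vaccine-eligible children (group A) with non-eligible children (group B) within each cluster, which cancels features shared by both groups, such as diagnostic performance. An RTS,S entry appears almost only on the forms of group A children in RTS,S clusters, so status-driven coding falls on exactly the contrast that estimates the vaccine effect. At stake is the credibility of any VA-based statement about malaria deaths.

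**Working it through.** **1. Reading the documents together.** The physician route works from the VAs, the VA form contains RTS,S status, and no step withholds that entry or the arm. Followed as written, the physician route is therefore unmasked coding. The algorithm route is the only one named in the protocol and the impact CRF. The documents therefore leave open which route will produce the cause-specific comparison.

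**2. Which outcomes can move.** Recoding from malaria to another illness leaves the death in the all-cause count and in the count that excludes injuries. Only a change between injury and non-injury could alter the primary outcome, and RTS,S status is unlikely to sway that decision. SAP Table 8 also reports deaths with and without the injury exclusion, so any effect would be visible. The exposed outcome is VA cause-specific mortality.

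**3. Scale, for illustration.** Inputs from SAP section 8, Table 5 and its footnotes: coverage c = 0.74; comparator-area coverage (contamination) d = 0.04; efficacy of 34% against severe malaria, also taken as the efficacy against malaria deaths, so Rv = 0.66. With no confounding, the SAP's dilution formula is

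R = (c·Rv + 1 − c) / (d·Rv + 1 − d).

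*Reproducing Table 5.* Severe malaria: numerator 0.74 × 0.66 + 0.26 = 0.748; denominator 0.04 × 0.66 + 0.96 = 0.986; ratio 0.759. Table 5 gives 0.75 and then 0.76. Mortality scenario a), Rv = 0.898: 0.924 and then 0.928. Table 5 gives 0.92 and then 0.93. The formula is reproduced.

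*Adding a coding shift.* Let x be the fraction of true malaria deaths in children known to be vaccinated that are coded to another cause. The documents give no value for x, so 5%, 10% and 20% are assumed. With no vaccine effect,

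R = (1 − c·x) / (1 − d·x).

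| x (assumed) | Calculation | Spurious R | R with true 34% efficacy |
|---|---|---|---|
| 0 | – | 1.000 | 0.759 |
| 5% | 0.963 / 0.998 | 0.965 | 0.735 |
| 10% | 0.926 / 0.996 | 0.930 | 0.711 |
| 20% | 0.852 / 0.992 | 0.859 | 0.663 |

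The last column uses [c·0.66·(1 − x) + 1 − c] / [d·0.66·(1 − x) + 1 − d]. At x = 10% the spurious reduction is 0.070 against an expected true reduction of 0.241, a ratio of 0.29. A shift toward malaria would bias the ratio upward instead.

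The calculation treats dose-1 coverage as the share of deaths with RTS,S visible to the coder. Where vaccination status is missing, the effect shrinks.

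**The case against.** The case for leaving the text alone has several parts.

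- **Nothing shows that coders see the status.** A reader might infer that physicians are handed RTS,S status. The documents do not say which fields reach a coder, and protocol 9.6 leaves anonymisation steps to country-specific protocols. This objection stands: the supportable statement is that the form carries the status and no masking is specified. It does not close the gap, because the SAP sentence refers to the VAs without qualification.
- **Physician coding may never be used.** It appears in one SAP sentence, as one of two options. This stands as a limit on scope, but it leaves an unreconciled difference over method.
- **The hospital comparison is weaker than it looks.** A reader might infer that blinded review is a guaranteed safeguard for hospital cases that the VA process lacks. It is something that may be done, and it depends on access to records beyond the CRF. The contrast is one of stated standard only.
- **The outcome is peripheral.** The SAP's secondary objectives take malaria deaths from hospital diagnosis, and neither Table 8 nor Annex 3 lists a VA malaria-death analysis. Limited VAs give no cause beyond accident or injury. All this is correct. The objective nevertheless remains in protocol 8.2.2, and protocol 9.4 says that VA results will feed it.
- **The coding shift is invented.** It is an assumption, and the table shows only what each value would imply.

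**Conclusion.** The point holds as a gap in specification with limited reach. If physician coding is used for the protocol's secondary VA cause-specific mortality objective, nothing in either document protects the comparison from coding that depends on vaccine status. An assumed shift of 5% to 20% would give a rate ratio of about 0.965 to 0.859 with no true effect, beside an expected value of about 0.76. That range rests on the SAP's 74% coverage and 4% contamination, on RTS,S status being visible for every vaccinated child who dies, and on a shift away from malaria. None of these is established for VA coding.

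A reader might go further and conclude that the primary mortality result is at risk. The documents do not support that: all-cause mortality does not depend on which illness is coded, and the injury exclusion is unlikely to be influenced. The change is worth making because it is cheap beforehand and, once unmasked coding is complete, can be repaired only by recoding.

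**What to change.** Reconcile SAP section 2 with protocol 9.3 and 9.4 on who assigns cause of death, and state one of the following.

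1. An algorithm that does not use RTS,S status or arm is the primary coding method for between-arm comparisons. Physician coding, if done, is supportive.
2. Records given to physician coders omit RTS,S entries, cluster and arm, and the location and facility fields that could identify arm (for example items 10055, 10057 and 10434). They are re-linked after coding.

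Under option 2, keep the other vaccine history. Items 10428 to 10431 cover all vaccines, and a coder who is weighing measles, tetanus or pertussis needs that information. Item 10431 is a single free-text entry, but the impact CRF holds separate date fields for each vaccine, so a coder-facing copy can carry the other recorded vaccines without RTS,S.

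The cost is a small export step and a few sentences in each document, with no new data collection. Masking under option 2 may be imperfect where narrative text reveals location, and the report should say so.
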